#### 7.1.4.1 Adverse Events of Special Interest

Adverse events of Special Interest (AESI)s are a pre-defined list of adverse events that are of potential immune-mediated medical conditions; the list can be found in Appendix 2.

Subjects will be assessed at each clinic visit and safety phone call for any new medical events or signs or symptoms that could possibly indicate an AESI. The subject will be asked whether any new diagnosis has been given to the subject through a review of recent medical history. Should a qualified healthcare professional who is not the investigator suspect a potential AESI, she/he should promptly inform the investigator.

A diagnosis of an AESI is to be reported in the same manner and time frame as an SAE and will be captured on the AE eCRF. If the eCRF is not available, then the study site must complete the paper SAE Report Form and send it to the Sponsor's Pharmacovigilance and Risk Management (PVRM) (or delegate) at [contact]. The investigator must notify the Sponsor within 24 hours. The AESI diagnosis, as well as if any medication is taken to treat the condition, will be recorded in the subject's source documents and on the AE eCRF and, as applicable, the Concomitant Medication eCRF.

### 7.1.5 Methods for Recording Adverse Events and Serious Adverse Events

Findings regarding AEs must be reported on an AE eCRF, as specified in Section 7.1.2, Unsolicited Adverse Events. All findings in subjects experiencing AEs must be reported also in the subject's source document.

All SAEs which occur during the course of the study, whether considered to be associated with the study vaccination or not, must be documented on the AE eCRF within 24 hours of the site becoming aware of the event.

If the eCRF is not available, then the study site must complete the paper SAE Report Form and send it to the Sponsor's PVRM (or delegate) at [contact] within 24 hours of becoming aware. Once the eCRF is available, the SAE should be documented on the AE eCRF as soon as possible.

Any medication or other therapeutic measures used to treat the AE will be recorded on the appropriate eCRF(s) in addition to the outcome of the AE.

After receipt of the initial report, representatives of the Sponsor or its designee will contact the investigator if it is necessary to obtain further information for an assessment of the event.

All SAEs must be reported by the investigator to his/her corresponding EC/IRB or applicable regulatory authorities in accordance with institutional policy/regulatory requirements and adequate documentation of this notification must be provided to the Sponsor.

Sponsor or its designee must also comply with the applicable regulatory requirement(s) related to the reporting of suspected unexpected serious adverse vaccine reactions (SUSARs) to the regulatory authority(ies) and the IRB/EC. If a SUSAR or other safety signal relating to the use of one of the study vaccines is reported to the Sponsor or its designee, the Sponsor will communicate the information to the investigator and the investigator will be responsible for submitting this information to the EC/IRB and other relevant authorities.

#### 7.1.5.1 Post-Study Events

Any SAE that occurs outside of the protocol-specified observation period or after the end of the study but is considered to be caused by the study vaccine will be processed by the Sponsor PVRM (or delegate) and must be reported using the email address: [contact].

These SAEs will be considered as part of the spontaneous reporting towards the investigational study vaccine in order to ensure the safety of all subjects.

#### 7.1.6 Pregnancies

If a subject becomes pregnant after vaccination, confirmation of pregnancy should be recorded in the eCRF. To ensure subjects' safety, each pregnancy in a subject after study vaccination must be reported to the Sponsor's PVRM (or delegate) within 72 hours of the site learning of its occurrence. The study site must complete the paper Pregnancy Reporting/Outcome Form and send it to [contact]. If the subject agrees to submit this information, the pregnancy must be followed to determine the outcome, including spontaneous or voluntary termination, details of the birth, and the presence or absence of any birth defects, congenital abnormalities, or maternal and/or newborn complications. This follow-up should occur even if the intended duration of safety follow-up for the study has ended.

Any pregnancy outcome meeting the definition of a SAE (see Section 7.1.4, Serious Adverse Events) must also be reported on the AE eCRF.

#### 7.1.7 Safety Laboratory Measurements

No scheduled safety laboratory measurements are planned for this study.

### 7.2 Efficacy Assessment

There is no assessment of efficacy in this study.

# 7.3 Immunogenicity Assessment

The measures of immunogenicity used in this study are standard, i.e., widely used and generally recognized as reliable, accurate, and relevant (able to describe the quality and extent of the immune response).

The immunogenicity analysis will evaluate the immunogenicity of the study vaccine, which will be measured by the HI and MN assay by titrating antibodies against the homologous influenza strains.

For the primary immunogenicity objectives, HI antibody responses using a cell-derived target virus will be evaluated for all strains. In case of a lack of agglutination for a specific strain using HI assay, immunogenicity for that strain will be assessed as measured by the MN assay.

For the secondary immunogenicity objectives, HI and MN antibody responses using cellderived target virus will be evaluated for all strains. In case of a lack of agglutination for a specific strain using HI assay, immunogenicity for that strain will be assessed as measured by the MN assay only.

For the exploratory immunogenicity evaluation, HI antibody responses may be evaluated for all strains using egg-derived and cell-derived target viruses. For the exploratory objective related to immunogenicity against heterologous strains MN assays and cell-derived target viruses will be used.

Testing will be conducted by the Sponsor or designated laboratory in a blinded manner towards the treatment arm.

# 8 STATISTICAL CONSIDERATIONS

A complete description of the statistical analyses and methods will be available in the Statistical Analysis Plan (SAP), which will be drafted before the first subject is enrolled and finalized before the database is locked for the primary analysis. The primary analysis will be conducted on the immunogenicity and safety data collected up to Day 29.

# 8.1 Endpoints

### 8.1.1 Primary Endpoint(s)

The primary objective of the study is to assess the immunogenicity of aQIVc formulations in comparison with QIVc vaccine, as measured by HI assay using cell-derived target viruses, and to assess the reactogenicity of different aQIVc formulations in comparison to QIVc for 7 days after vaccination and the safety of all vaccines for 28 days after vaccination.

## 8.1.1.1 Primary Immunogenicity Endpoints

Humoral immune response of the aQIVc formulations in comparison with the QIVc vaccine in terms of HI antibody response against homologous vaccine strains:

- Geometric Mean Titer (GMT): Geometric mean of HI antibodies at Day 1 and Day 29.
- Geometric Mean Fold Increase (GMFI): The Geometric mean of the fold increase in serum HI titer post-vaccination (Day 29) compared to pre-vaccination (Day 1).
- Percentages of subjects with HI titers  $\geq$  1:40 at Day 1 and Day 29.
- Percentage of subjects with seroconversion (defined as a ≥4-fold increase in titer postvaccination in those with pre-vaccination titer above the LLOQ (1:10), or a postvaccination titer ≥1:40 for subjects with baseline titer below the LLOQ (1:10) for HI antibodies at Day 29).

Note that the HI assay could be replaced by the MN assay due to a lack of agglutination.

Derived variables at Day 29:

- The GMT ratio (aQIVc formulation/QIVc) for each strain.
- The inter-group difference in the SCRs (aQIVc formulation minus QIVc) for each strain.

• The inter-group difference in the percentage of subjects with HI titer ≥1:40 (aQIVc formulation minus QIVc) for each strain.

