#### 8.1.2.1 Secondary Immunogenicity Endpoints

Humoral immune response of the aQIVc formulations in comparison with the QIVc vaccine in terms of HI antibody response against homologous vaccine strains:

- GMT: Geometric mean of HI antibodies at Day 181.
- GMFI: The Geometric mean of the fold increase in serum HI titer post-vaccination (Day 181) compared to pre-vaccination (Day 1).
- Percentages of subjects with HI titers  $\geq$ 1:40 on Day 181.

Derived variables:

- The GMT ratio (aQIVc formulation/QIVc) for each strain.
- The inter-group difference in the percentage of subjects with HI titer ≥1:40 (aQIVc formulation minus QIVc) for each strain.

Confidential

Effective Date: See System Metadata

In addition, the humoral immune response of the aQIVc formulations in comparison with the QIVc vaccine in terms of MN antibody response against homologous vaccine strains:

- GMT: Geometric mean of MN antibodies at Days 1, 29 and 181.
- GMFI: The Geometric mean of the fold increase in serum MN titer post-vaccination (Day 29 and Day 181) compared to pre-vaccination (Day 1).
- Percentages of subjects with seroconversion (defined as ≥ 4-fold increase for subjects with pre-vaccination MN titers ≥ Lower Limit of Quantitation (LLOQ) or as ≥ 4LLOQ for subjects with pre-vaccination MN titer <LLOQ) at Day 29.

Derived variables:

- The GMT ratio (aQIVc formulation/QIVc) for each strain
- The inter-group difference in the SCRs (aQIVc formulation minus QIVc) for each strain.

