# 8.6 Subgroups

All analyses (safety and immunogenicity) will be done by the age subgroups  $\geq$ 50-64 years or  $\geq$ 65 years.

Unadjusted and adjusted immunogenicity analysis of the GMTs will be performed by the following subgroups:

- Influenza vaccination history previous 3 years as yes and no, where we excluding this factor in the analysis model;
- Comorbidity risk (yes/no) defined as the Comorbidity Risk Score (by Hak et al.) < 50 (comorbidity risk = no) or ≥50 (comorbidity risk = yes);
- Sex;
- Country;
- Pre-vaccination status HI or MN < 1:10 (or LLOQ) and HI or  $MN \ge 1:10$  (or LLOQ)...

The adjusted GMT subgroup analysis will not be conducted if , the number of subjects in a subgroup category is less than 10% of the total population.

Exploratory interaction analyses may be conducted to support consistency or lack of consistency of the results among the subgroups.

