#### **Immunogenicity**

Values below the lower limit of quantification will be set to half that limit. Values above the upper limit of quantification will be set to the value of this upper limit.

**Seroconversion** based on **HI** antibodies is defined as binary variable for subjects with non-missing values pre-vaccination- and post-vaccination as:

= 1, if seroconverted (defined as  $a \ge 4$ -fold increase in titer post-vaccination in those with prevaccination titer above the LLOQ (1:10), or a post-vaccination titer  $\ge 1:40$  for subjects with prevaccination titer below the LLOQ (1:10))

= 0, otherwise

**Seroconversion** based on **MN** antibodies is defined as binary variable for subjects with nonmissing values pre-vaccination- and post-vaccination as:

26 Augustus 2021 Final Version 2.0

= 1, if seroconverted (defined as a  $\geq$  4-fold increase in titer post-vaccination in those with prevaccination titer above the LLOQ, or a post-vaccination titer  $\geq$  4 times the LLOQ for subjects with pre-vaccination titer below the LLOQ

= 0, otherwise

Fold increase is defined as the post-vaccination titer divided by the pre-vaccination titer.

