# **11.2 Primary Objectives Analysis**

The primary endpoints in terms of HI antibody response against homologous vaccine strains are defined as:

- Geometric Mean Titer (GMT): Geometric mean of HI antibodies at Day 1 and Day 29.
- Geometric Mean Fold Increase (GMFI): The Geometric mean of the fold increase in serum HI titer post-vaccination (Day 29) compared to pre-vaccination (Day 1).
- Percentages of subjects with HI titers  $\geq$  1:40 at Day 1 and Day 29.
- Percentage of subjects with seroconversion (defined as a ≥4-fold increase in titer post-vaccination in those with pre-vaccination titer above the LLOQ (1:10), or a post-vaccination titer ≥1:40 for subjects with baseline titer below the LLOQ (1:10) for HI antibodies at Day 29).

Note that the HI assay could be replaced by the MN assay in case of a lack of agglutination.

In addition, reverse cumulative distribution plots will be generated to display the distribution of the antibody responses at Day1 and Day 29 for each of the vaccine groups. The x-axis represents the immunogenicity values, and the scale of the axis is logarithmic. The y-axis represents the

percentage of subjects having at least that immunogenicity value. Due to the discrete values of antibody response, the plot will show a step-wise function. The figures begin at 100%, and then descends to the lowest point on the curve, which is the percentage of subjects having an immunogenicity value equal to the highest observed value.

All statistical analyses will be descriptive in nature. No hypothesis testing will be applied.

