# 11.3 Secondary Objectives Analysis

The secondary endpoints in terms of HI antibody response against homologous cell-derived vaccine strains (A/H1N1, A/H3N2, B/Yamagata and B/Victoria) at Day 181, are:

- GMT: Geometric mean of HI antibodies at Day 181;
- GMFI: The Geometric mean of the fold increase in serum HI GMTs post-vaccination (Day 181) compared to pre-vaccination (Day 1);
- Percentages of subjects with HI titers  $\geq$  1:40 on Day 181.

In addition, the humoral immune response in terms of MN antibody response against homologous cell-derived vaccine strains (A/H1N1, A/H3N2, B/Yamagata and B/Victoria) at Days 1, 29 and 181:

- GMT: Geometric mean of MN antibodies at Days 29 and 181;
- GMFI: The Geometric mean of the fold increase in serum MN GMTs post-vaccination (Day 29 and Day 181) compared to pre-vaccination (Day 1);

• Percentages of subjects with seroconversion (defined as ≥ 4-fold increase for subjects with prevaccination MN titers ≥ Lower Limit of Quantitation (LLOQ) or as ≥ 4\*LLOQ for subjects with pre-vaccination MN titer <LLOQ) at Day 29.

The analysis of the secondary immunogenicity endpoints will be conducted in the same way as described for the primary immunogenicity endpoints.

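### HI seroconversion is undefined for a baseline of exactly 1:10, and SAP 8.8 codes those subjects as failures; for MN, SAP 8.8 contradicts SAP 11.3

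*Protocol*

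**What the plan says.** **HI.** Protocol 8.1.1.1 makes Day 29 seroconversion a primary endpoint and the inter-group SCR difference a derived primary variable for each strain. The 4-fold criterion applies "in those with pre-vaccination titer above the LLOQ (1:10), or a postvaccination titer ≥1:40 for subjects with baseline titer below the LLOQ (1:10"). SAP 11.2 repeats this: "in those with pre-vaccination titer above the LLOQ (1:10), or a post-vaccination titer ≥1:40 for subjects with baseline titer below the LLOQ (1:10"). SAP 8.8, which defines the analysis variable, has the same upper branch ("increase in titer post-vaccination in those with prevaccination titer above the LLOQ (1:10), or a post-vaccination titer" of at least 1:40 below the limit). It covers all subjects with non-missing pre- and post-vaccination values and codes as 0 anyone who meets neither branch.

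**MN.** SAP 8.8 again uses a strict inequality: "increase in titer post-vaccination in those with prevaccination titer above the LLOQ, or a post-vaccination titer" of at least four times the LLOQ for lower baselines. Protocol 8.1.2.1 instead says "4-fold increase for subjects with pre-vaccination MN titers ≥ Lower Limit of Quantitation (LLOQ"), and SAP 11.3 says "4-fold increase for subjects with prevaccination MN titers ≥ Lower Limit of Quantitation (LLOQ"). Protocol 8.1.1.1 lets MN replace HI for a strain that does not agglutinate.

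**Values at the limit.** SAP 8.8: "Values below the lower limit of quantification will be set to half that limit". Protocol 8.4.2.2.3 likewise sets only HI titers under 10 to 5. The protocol synopsis, under Statistical Analyses, describes the same substitution but writes the condition as less than or equal to the LLOQ. SAP 8.6 defines the lower baseline subgroup by "Pre-vaccination status HI or MN < 1:10 (or LLOQ) and HI or" MN at or above 1:10 (or LLOQ) as the upper one, so it counts the boundary as upper.

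**The concern.** A titer of exactly 1:10 is an attainable value: it is the limit itself and is not halved under protocol 8.4.2.2.3 or SAP 8.8. Such a subject is neither above nor below the LLOQ, stays in the denominator, and falls to the residual code 0 whatever the Day 29 titer.

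The Day 29 read-out informs Phase 3 development (protocol 8.6), and SCR is one of the primary measures it rests on. For MN, a programmer following SAP 8.8 and one following SAP 11.3 could report different SCRs from the same data. If MN replaced HI for a strain, that disagreement would reach a primary endpoint.

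**Working it through.** **Figures in the plan.** The plan gives no expected SCR and no SCR-based power, so there is no stated figure to reproduce for this endpoint. The protocol's Table 8-1 is based on GMT and does not use the rule; it reproduces with the noncentral t distribution (n = 95 per group, SD 0.7: 83.86% and 23.08% at a GMT ratio of 2.00).

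**Step 1: the rule case by case.** Every baseline and Day 29 pair was coded on an assumed two-fold grid (5, 10, 20, ..., 2560).

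| Baseline | Day 29 | SAP 8.8 as written | 4-fold branch at or above 10 |
|---|---|---|---|
| 5 | 40 | 1 | 1 |
| 10 | 20 | 0 | 0 |
| 10 | 40 | **0** | **1** |
| 10 | 640 | **0** | **1** |
| 20 | 80 | 1 | 1 |

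The two rules differ in 7 pairs, all with baseline 10 and Day 29 titer of 40 or more, and always as 0 against 1. No pair goes the other way, so an arm's SCR can only fall or stay equal. Moving 1:10 into the lower branch instead gives identical results (0 differing pairs), because 4 × 10 = 40. For MN, a baseline equal to the LLOQ with a post-vaccination titer of at least 4 × LLOQ is coded 0 by SAP 8.8 and 1 by SAP 11.3.

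**Step 2: expected loss per arm.** Loss in SCR = s × q, where s is the share of subjects at exactly 1:10 and q is the share of those reaching 1:40. The documents give neither, so the values below are assumptions. With q = 0.60 for aQIVc, q = 0.40 for QIVc and the same s in both arms (for example 0.10 × 0.60 = 6 points):

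| s | aQIVc loss (points) | QIVc loss (points) | Mean fall in difference (points) |
|---|---|---|---|
| 5% | 3 | 2 | 1 |
| 10% | 6 | 4 | 2 |
| 15% | 9 | 6 | 3 |
| 20% | 12 | 8 | 4 |

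With equal response in the two arms (50% and 50%), the expected change in the difference is 0.

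**Step 3: one observed difference.** The number of responders lost is X ~ Bin(95, 0.6s) for aQIVc and Y ~ Bin(95, 0.4s) for QIVc, independent, with 95 evaluable per group (protocol 8.5).

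| s | Shrinks, P(X>Y) | Equal, P(X=Y) | Widens, P(X<Y) |
|---|---|---|---|
| 5% | 0.58 | 0.17 | 0.25 |
| 10% | 0.68 | 0.11 | 0.21 |
| 15% | 0.74 | 0.08 | 0.18 |
| 20% | 0.79 | 0.06 | 0.15 |

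At s = 5% the chance that an arm loses nobody is 0.97^95 = 0.055 (aQIVc) and 0.98^95 = 0.147 (QIVc), so not every SCR need fall.

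**Step 4: scale.** For an illustrative 57/95 against 38/95, the difference is 20.0 points with a Miettinen-Nurminen 95% CI of 5.8 to 33.4. The half-width is (33.4 − 5.8)/2 = 13.8 points, larger than the 1 to 4 points above.

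**Step 5: if the synopsis rule governed.** A baseline of 10 would become 5 and enter the lower branch, and the coding would match the repaired rule (0 differing pairs). GMFI would instead be multiplied by 2^(p1 − p29), where p1 and p29 are the shares at exactly 10 on Day 1 and Day 29. For p1 = 5/10/15% that is +3.5/7.2/11.0% if p29 = 0, and +2.1/5.7/9.4% if p29 = 2%. The Day 1 part should be similar across arms under randomization. The SCR loss and this effect are alternatives; they cannot both apply.

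**The case against.** The strongest reply is that the intent is recoverable. SAP 8.6, SAP 11.3 and protocol 8.1.2.1 all put the boundary in the upper group, and either placement of 1:10 gives the same result. A programmer who noticed the gap would therefore resolve it correctly. The plan does not say that SAP 8.8 takes precedence over the endpoint definitions, and the MN route to a primary endpoint also requires a strain to fail to agglutinate. The shares used for the size are assumed; no dilution series or numeric MN LLOQ is given. No hypothesis is tested, no success criterion is set, and the assumed shift in the difference is small against its confidence interval. The synopsis wording looks like a slip, and under it the GMTs and the baseline covariate would change as well as GMFI.

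Most of this stands as a limit on importance. It does not remove the defect. For HI, all three definitions share the gap, and the only explicit instruction for a subject in neither branch is to code 0. For MN, two sections of the same SAP give opposite codes. Relying on a programmer to notice means the result does not follow from the plan as written. The point about GMTs under the synopsis rule is correct, and is a further reason to align that wording.

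**Conclusion.** The concern holds. As written, the HI rule codes a baseline of exactly 1:10 as a non-response whatever the Day 29 titer, and SAP 8.8 contradicts SAP 11.3 and protocol 8.1.2.1 for an MN baseline equal to the LLOQ. This follows from the text and the enumeration, given that protocol 8.4.2.2.3 and SAP 8.8 govern the halving rather than the synopsis.

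The direction is certain for each arm's SCR (down or unchanged) but not for the difference between arms, which shrinks on average only if aQIVc responds better among subjects at 1:10. The size is conditional on the assumed shares and could be settled only from baseline data. The matter should be fixed, but it does not threaten the study: the GMT analyses, the percentage at or above 1:40 and the sample size are unaffected by the seroconversion rule.

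**What to change.** In protocol 8.1.1.1, SAP 8.8 (HI and MN) and SAP 11.2, apply the 4-fold branch to a pre-vaccination titer at or above the LLOQ, and the other branch to a titer below it. This matches protocol 8.1.2.1, SAP 11.3 and SAP 8.6. A baseline of 1:10 then needs at least 1:40, the same threshold as a baseline below the LLOQ, so the rule has no jump at the boundary. In the synopsis, make the halving condition strictly below the LLOQ, to agree with protocol 8.4.2.2.3 and SAP 8.8.

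The cost is one comparison in each definition and in the derivation program, with no new data. It should be settled before unblinding for the Day 29 analysis. The protocol wording would go through the change process in protocol 13.4. Correcting SAP 8.8 and recording it in SAP 16 would by itself secure the programmed result, with SAP 11.2 aligned at the same time.

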#### 8.1.1.2 Primary Safety Endpoints

- Solicited local or systemic AEs for 7 days following vaccination (Day 1 through Day 7), based on the subject reported data (eDiary).
- Severe solicited local or systemic AEs for 7 days following vaccination (Day 1 through Day 7), based on the subject reported data (eDiary).
- Unsolicited AEs for 28 days following vaccination (Day 1 to Day 29).
- SAEs, MAAE, AEs leading to withdrawal from the study, AESIs for 28 days after vaccination (Day 1 to Day 29).

#### 8.1.2 Secondary Endpoints

Secondary endpoints evaluated in the study include a safety assessment of all vaccines for 180 days after vaccination and the immunogenicity endpoints measured by the HI assay assessed at Day 181 and the immunogenicity endpoints measured by the MN assay both at Day 29 and Day 181. Also, the solicited systemic events and injection site pain (both any and severe) will be assessed using the investigator evaluation (see section 7.1.1 Solicited Adverse Events).

